We will enroll 68 subjects with pulmonary arterial hypertension Class 1,3,4 and 5 (Nice 2013) with symptoms consistent with NYHA Class I-III.

Inclusion criteria

- Men and women age 18 or older not greater than age 65 years
- Diagnosis of pulmonary arterial hypertension class 1,3,4 and 5 (Nice 2013)
- NYHA/WHO Class I-III
- PAH medications must have been initiated according to the latest consensus statement recommendations and remained stable for the last 30 days
- Women of child-bearing age must use a double-barrier local contraception till completion of the study

- Subjects must demonstrate understanding of the study, sign the informed consent, and have a reliable method of communication for contact and ability to comply with the study requirements.

Exclusion criteria

- Participation in any other treatment studies during enrollment
- Significant illness in the past 30 days requiring hospitalization
- Hepatic insufficiency (transaminase levels >4 fold the upper limit of normal or bilirubin >2 fold the upper limit of normal),
- History of HIV, Hepatitis B or C
- Serum creatinine >2.8 mg/dl
- Pregnancy, breast-feeding, or lack of safe contraception
- Acute decompensated heart failure within past 30 days
- Known allergy or intolerance to carvedilol or other β blockers
- Significant, persistent bradycardia (resting heart rate <50 bpm) or hypotension (systolic blood pressure <100 mmHg or mean blood pressure <70 mmHg) at the time of enrollment
- Second or third-degree AV block without pacemaker
- Use of hypotensive drugs that deplete catecholamines (such as reserpine and monoamine oxidase inhibitors) which may lead to greater signs of hypotension or bradycardia
- Use of amiodarone, diltiazem, verapamil, clonidine
- Active bronchospasm
- Other medical and psychosocial conditions as determined by principal investigator deemed unsuitable for enrollment

C. Sample Size Rationale and Estimate

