Target enrollment for this study will be 68 patients. The primary outcomes FDG-PET uptake and erythropoietin, are anticipated to have positively skewed distributions, amenable to the use of ratios of 6-month measures relative to baseline to measure changes over time. Log transformed ratios are then anticipated to have approximately normal distributions. For secondary measures demonstrating less skewness or even approximate normality without the log transformation, absolute changes from baseline to 6 months will be used to measure change over time. Sample size is determined taking into account the power of the T-test for comparing the placebo and low dose carvedilol groups with respect to the reduction in FDG-PET uptake, as measured by the ratio of 6-month uptake to baseline uptake. Variability in FDG-uptake measures over 6 months suggests an expectation that the coefficient of variation in uptake ratios will not exceed 50%. Using a Bonferroni correction to adjust for multiple time points with $\alpha=0.025$, the T-test comparing log-ratios has 90% power to detect a difference in groups such that ratios have a 50% lower median for the low dose carvedilol group relative to the placebo group, if the groups contain $n=14$ subjects each. This effect size was selected based on previously observed reductions in FDG-PET uptake of roughly 50% among patients on β -blocker. Considering 10% potential dropout after randomization and a 30% potential dropout during the run-in phase, we intend to enroll 68 patients into the run-in phases, to achieve at least 48 patients eligible for randomization into the placebo, low dose Carvedilol, or dose escalation groups.

D. Enrollment

Recruitment Strategy

Patients who are diagnosed with PAH will be identified as potential subjects by either a nurse or doctor involved in the patient's disease management. These patients will be referred to the study investigators for screening and to obtain informed consent. Subjects will be recruited as they become available and without regard to gender, race, or ethnicity.

Informed Consent

All volunteers will be approached by the study investigators or their designee. The consent interview will take place the day of a patient visit to the Pulmonary Department. In a private examination room, one of the research investigators will explain the details of the study, to the

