Final eligibility will be determined by the investigator after review of the medical record and data gathered during the screening visit. Eligible, enrolled subjects will undergo additional baseline procedures:

- Quality of life questionnaires
- Fasting Gated FDG-PET scan
- Echocardiography
- Blood draw for flow cytometry, plasma nitrite and nitrate, global arginine bioavailability ratio (GABR), Erythropoietin, & NT-proBNP
- Urine for nitrate
- Exhaled NO

E. Intervention

Open-label Run-in Phase

All enrolled, eligible subjects will receive an open-label carvedilol therapy at starting dose of 3.125 mg twice daily for one week and be monitored at the Clinical Research Unit for the first-dose challenge of Carvedilol. Upon discharge, enough carvedilol to complete the 1-week run-in period will be dispensed by a licensed provider. Subjects will be instructed to return in 1 week with any

unused medication. Those individuals who are eligible for randomization to the trial will undergo the procedures summarized in Table A1 “Run-in Week”.

Double-blinded Randomized Phase

At the end of the 1-week run-in phase, subjects who have tolerated the low-dose carvedilol without severe or limiting side effects, still meet the inclusion and exclusion criteria, and who wish to continue in the study will be randomized to one of three arms: placebo, low-dose carvedilol, or escalating dose carvedilol for 6 months. Subjects and the investigators will be blinded to their group assignment for the duration of the study.

- Group 1 will receive a placebo drug to take twice daily for 6 months.
- Group 2 will receive carvedilol at a dose of 3.125 mg twice a day for 6 months.
- Group 3 will receive carvedilol in a dose escalation scheme. They will be given 3.125 mg tablets to take bid for 1 week, followed by 6.25 mg bid for 1 week, followed by 12.5 mg bid for 1 week with the option to increase to the max dose of 25 mg bid for the remainder of the study. During up titration, if a dose is not tolerated, the dose will be decreased to the previous tolerated dose for the remainder of the study.

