Because study physicians are blinded to groups, if patients are determined to be intolerant of drug (based on symptoms, signs such as sitting systolic BP<85 mm Hg or resting pulse<50, or severe adverse event such as hospitalization for heart failure), a request for dose reduction to the prior week will be requested from the research pharmacist ([name]), who is aware of treatment assignment. He will provide a new week's worth of medications at the “lower” dose. In the case of placebo, placebo will again be provided. In the case of fixed low-dose of carvedilol, placebo will be provided. In the case of dose-escalating carvedilol, the prior week's dose will be provided. Regardless of changes in dose, all three randomized study groups will be compared, based on the intent-to-treat principle, and thus subjects will be maintained in their original assigned study group for analyses.

Randomization scheme

Blocked randomization will be used. The block sizes will also be random and known only to the research pharmacist ([name], Cleveland Clinic Research Pharmacy), who will perform the randomization and know treatment assignment at time of enrollment. The research pharmacist will ensure that a disproportionate subclass (idiopathic, familial or associated PAH) and/or severity of PAH are not entered into any single arm of the study.

Blinded Medication Dispensing

After randomization, all subjects will receive the study medication/placebo for the first 4 weeks in 4 separate bottles labeled “week 1,” “week 2,” “week 3” and “week 4” to blind subjects to whether they are assigned to the dose escalation group. All pills will be encapsulated so that dosing or medication cannot be discerned by patients or study investigators. Enough medication/placebo will be dispensed to last until the next scheduled follow-up visit. Subjects will be instructed to bring all unused medication and the medication bottles (even if empty) to each follow-up visit.

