Baseline characteristics will be reported, including age range and the proportions that are female, postmenopausal, and Caucasian. Means and standard deviations or medians and interquartile range will be reported for all continuous data, and non-continuous data will be reported as percentages. A log transformation may be utilized for any data that is not normally distributed. The three randomized study groups will be compared, based on the intent-to-treat principle, with respect to changes from baseline. Repeated measures analysis of variance will be used to compare groups using data from all time points together, though T-tests will also be used to compare pairs of groups with respect to differences between pairs of time points. Using actual administered doses, relationships between dose and changes over time will also be explored using appropriate linear or non-linear models to estimate dose-response relationships. Reports of blinded group summaries of adverse events will be regularly produced for safety monitoring.

b. Confidentiality

To maintain patient confidentiality, all study data will be de-identified. Each subject, upon enrolling in the study, will be assigned a three-digit subject number. Case report forms and the study database will identify each subject only by subject number and will contain no patient identifiers. De-identified case report forms will be kept within study binders, kept in a locked filing cabinet in a locked room. Completely de-identified study data will be stored in a data table maintained on a password-protected computer and stored on the Cleveland Clinic network, which is regularly backed up. The code identifying which patient belongs to each subject number will be kept in a separate locked filing cabinet in a locked room. Only the study coordinator and investigators will have access to this code.

REFERENCES

1. ATS statement: guidelines for the six-minute walk test. Am J Respir Crit Care Med 2002;166:111-7.

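### Blocked randomisation alone cannot deliver the balance in PAH subclass and severity that the pharmacist must ensure, and the analysis plan includes neither factor

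*Combined protocol and SAP*

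**What the plan says.** The section Randomization scheme of the combined protocol and SAP gives one allocation method: "Blocked randomization will be used". Block sizes are random and known only to the research pharmacist, "who will perform the randomization and know treatment assignment at time of enrollment". The next sentence says that the same person "will ensure that a disproportionate subclass (idiopathic, familial or associated PAH) and/or severity of PAH are not entered into any single arm".

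No section names strata, a minimisation rule, a threshold for what counts as disproportionate, or a measure of severity to be used for allocation. The wording also leaves open whether one factor or both must be balanced. Section B, Population, admits Nice 2013 classes 1, 3, 4 and 5, and the three subclasses named for balance are not mapped to those classes.

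Under Data Analysis/Reporting, the Analysis Plan compares the three groups by repeated measures analysis of variance and adds that "T-tests will also be used to compare pairs of groups with respect to differences between pairs of time points". Neither subclass nor severity appears as a covariate or stratum.

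On blinding, the section Double-blinded Randomized Phase states: "Subjects and the investigators will be blinded to their group assignment for the duration of the study".

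**The concern.** The stated method and the stated duty do not fit together. Permuted blocks keep the arms equal in number. They do nothing for disease subclass or severity unless the blocks are run within strata. Someone who must nevertheless ensure balance needs either a rule that the protocol does not give or freedom to choose among assignments whose arms are known.

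This matters because the planned group comparisons assume that assignment follows a fixed chance rule. A reader of the protocol cannot confirm that it does.

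There is a second, smaller consequence. If balance is achieved by design and the analysis ignores the balancing factors, the standard error of the unadjusted T-test is too large to the extent that the factors predict change.

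**Working it through.** **Inputs from the documents** (section C, Sample Size Rationale and Estimate): 14 per group; alpha 0.025; 90% power; a 50% lower median ratio; coefficient of variation (CV) of the ratios at most 50%; 10% dropout after randomisation; at least 48 randomised.

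**Assumptions:** equal allocation, a two-sided test, the subgroup sizes, and R², the share of within-arm variance in the log-ratio that the factors explain. The documents give none of these.

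**1. The plan's own figure.** The section states that "the T-test comparing log-ratios has 90% power to detect a difference in groups such that ratios have a 50% lower median" with 14 per group. On the log scale the difference is ln 2 = 0.693.
- If the SD is √ln(1 + 0.5²) = 0.472, the effect is 0.693/0.472 = 1.467 SD. Noncentral-t power at 14 per group is 92.6%.
- If the CV is taken directly as the log SD of 0.5, the effect is 1.386 SD and power is 89.4%.

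The stated 90% reproduces. For the randomised total, 14/0.9 = 15.6, so 16 per arm, and 3 × 16 = 48.

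**2. What blocking alone achieves.** With K subgroup patients among 48 and 16 per arm, the chance of a, b and c of them in the three arms is C(16,a)·C(16,b)·C(16,c)/C(48,K). Summing exactly:

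| K | Placebo vs low dose, 3 or more | Placebo vs low dose, 4 or more | Any two arms, 3 or more | Any two arms, 4 or more |
|---|---|---|---|---|
| 12 | 31% | 16% | 53% | 32% |
| 16 | 35% | 19% | 64% | 40% |
| 20 | 38% | 21% | 66% | 43% |
| 24 | 38% | 22% | 62% | 43% |

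For comparison, blocks of 3 and 6 (sizes chosen only for the calculation) run within four strata from two binary factors were simulated. The any-two-arms figures fall to about 6-7% and 0.4-0.5% for each factor. The chance that at least one of the two factors is off by 3 or more is about 11%.

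**3. Balancing a factor and then leaving it out.** With exact balance, the variance of the difference in means is 2σ²(1 − R²)/n, but the unadjusted test estimates roughly 2σ²/n. The test statistic is therefore too small under the null. Simulation with one balanced binary factor, 14 per arm and an effect of 1.386 SD gives:

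| R² | True level, unadjusted | Power, unadjusted | Power, adjusted |
|---|---|---|---|
| 0 | 0.025 | 89% | 89% |
| 10% | 0.018 | 90% | 92% |
| 20% | 0.012 | 91% | 95% |
| 30% | 0.008 | 92% | 97% |

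The adjusted level stays at about 0.025 throughout. With two factors sharing the R², stratified blocks and 42 patients, the unadjusted level is 0.020, 0.014 and 0.009. Across 14 or 16 per arm and both readings of the CV, adjustment gains about 1 to 5 points of power for R² from 10% to 30%. At R² = 0 it costs about 0.5 point or less.

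**The case against.** The strongest reply is that this is an incomplete description and not a flawed design. A chance mechanism is stated, the sentences can be read as blocks prepared within strata, and nothing authorises a departure from the list. That stands as far as it goes. A reader might infer that the pharmacist will override the list or that allocation is not random, and the documents do not support that. What remains is that the stated method cannot produce the stated result, and the missing rule decides how patients are assigned.

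A reader might also infer from the missing covariates that the false-positive rate is inflated or that the trial is underpowered. Neither follows. The unadjusted test errs on the conservative side, and its power at the planned effect is about 89-92% for every R² considered. Adjustment offers a gain that the plan never promised, so leaving it out is not a shortfall.

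Three further points are fair:
- Nothing shows that subclass or severity predicts change. The outcome is each patient's own 6-month to baseline ratio, which already removes stable differences in level, so R² could be zero.
- The threshold of 3 patients is chosen here, because the documents set none.
- Section C powers only placebo against low dose, so 31-38% is the more relevant figure, and 53-66% applies to all three arms.

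**Conclusion.** The point holds as a gap between method and requirement. Blocking alone leaves a difference of 3 or more patients between placebo and low dose in about a third of allocations, for assumed subgroups of 12 to 24 among 48 equally allocated patients. The balance sentence therefore depends on a mechanism that the protocol does not state. These percentages show only that blocking cannot deliver what is required. They measure no bias, none is demonstrated, and concealment from investigators is intact.

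The analysis part is secondary and conditional. If the factors are balanced and explain 10%, 20% or 30% of variance, the true level is about 0.018, 0.012 or 0.008 against 0.025. Adjusting for them restores the nominal level. The power gain is an optional efficiency at the planned effect. The correction is worth making because it is cheap and settles how patients are allocated.

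**What to change.** Replace the sentence on ensuring balance with a stated rule: a computer-generated, concealed list using random permuted blocks, stratified by at most two defined binary factors. To keep the plan's own intent, these would be:
- disease subclass, collapsed into two categories so that every class admitted in section B falls in one of them;
- severity, for example baseline NYHA/WHO class in two categories, using the definitions already given under Data Collection.

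If more levels are wanted, or site (Study Design describes a multi-center trial, Data and Safety Monitoring a single-center one), use minimisation with a random element. Allow no manual departure from the list. The pharmacist can still hold it and dispense. Add the same factors as covariates to the comparisons in the Analysis Plan. If a stratified list already exists, state its factors and categories and adjust for them.

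**Cost:** protocol wording, a new or better described list, and 2 degrees of freedom. Incomplete blocks can leave arms unequal. With four strata, arm sizes differ by 4 or more in about 7-9% of simulated trials. With six strata the figure is about 18%, and with twelve (four classes by three functional classes) about 43%, which is why the factors need collapsing.

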This will be a double-blinded, randomized, controlled intervention with three arms preceded by an open-label 1-week run-in period. This is a multi-center trial with the Cleveland Clinic being the leading site. After screening and consent, all eligible patients will have their first visit at the Clinical Research Unit to start the open-label challenge of carvedilol at a dose of 3.125 mg twice daily. The patient will be monitored for at least 3 hours and if a patient tolerates this dose (assessed by symptoms and vital signs including blood pressure and pulse), a patient will then be discharged home to continue on the drug at 3.125 mg twice daily for the remainder of the week. Patients will receive a follow up phone call the day after their first randomization visit. Patients will be provided with a blood pressure monitor for home and will measure their blood pressure and pulse as directed, and will be contacted daily during the first week to check on vital signs and symptoms. Patients who are able to complete the 1-week run-in phase without adverse effects will return to clinic for assessment by history and physical exam. Stable patients will be randomized to one of three arms for 24 weeks of treatment with placebo, fixed low-dose Carvedilol, or dose-escalating carvedilol to maximum tolerated dose. The first group will receive a placebo drug for the remainder of the study. The second group will continue with carvedilol at a dose of 3.125 mg twice daily. The third group of patients will receive carvedilol 3.125 mg twice daily one week, then 6.25 mg twice daily for second week, 12.5 mg twice daily for third week with the option to increase to the maximal dose of 25 mg bid for the remainder of the study period. If a dose is not tolerated, the dose will be decreased to the prior week's tolerated dose for the remainder of the study. Subjects will receive weekly phone calls after starting the study and a study visit at weeks 1, and months 1, 3 and 6 to evaluate for side effects, to monitor clinical status, and to collect outcome data. Patients will be provided a home blood pressure monitoring device and asked to record pulse and blood pressure in the morning and evening with instructions to call at any time if systolic BP<85 mm Hg or pulse<55, or if there is any adverse event such as hospitalization or unscheduled doctor visits.

B. Population

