If any patients in any arm of the study appear intolerant of drug (based on symptoms such as persistent light-headedness, sitting systolic BP<85 mm Hg or resting pulse<50, or hospitalization for heart failure), they will be provided a new bottle of pills labeled “week-dose reduction” as following: subjects on dose-escalating carvedilol will be provided a new bottle of carvedilol at the prior week's dose, subjects on fixed low-dose of carvedilol will be provided placebo pills, subjects on placebo will be provided a new placebo pill bottle. Once dose reduction has occurred in the dose-escalating arm, subjects will be maintained on that set dose throughout the remainder of the study, with no further escalation of dose. If signs or symptoms of subjects in any arm persist despite the dose reduction, dose reduction will again be implemented as follows: subjects on dose-escalating carvedilol will be provided a new bottle of carvedilol at half the current reduced dose, subjects on fixed low-dose carvedilol will again be provided placebo pills, subjects on placebo will again be provided a new placebo pill bottle. Of note, only 3 total dose reductions will be allowed during the entire 6 month study. Following 3 dose reductions are implemented, if subjects are still intolerant, they will be removed from all study drug.

Subject Instruction

All subjects will be advised to take the study medication with a small meal. All subjects will receive a daily phone call for the first week after start of carvedilol during the run-in. Thereafter, patients will be called weekly to screen for side effects and to monitor their clinical status. Patients will be provided a home blood pressure monitoring device and asked to record pulse and blood pressure in the morning and evening at the same time each day with instructions to call at any time systolic BP<85 mm Hg or pulse<55. Lightheadedness is expected to occur, but in 99.5% of cases in prior studies of severe heart failure, this resolves without problems. Patients will be instructed to sit up and rise slowly. Patients will also be instructed to call if they experience any new or worsening symptoms, or require hospitalization or unscheduled doctor visits.

F. Follow-up Schedule

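### A week 1 dose reduction in the escalating arm leaves the dose at 3.125 mg bid, and in any arm the withdrawal rule for repeated reductions can cost intolerant patients their 6-month FDG-PET

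*Combined protocol and SAP*

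**What the plan says.** **Doses.** For the run-in, E. Intervention, Open-label Run-in Phase, states: "All enrolled, eligible subjects will receive an open-label carvedilol therapy at starting dose of 3.125 mg twice daily for one week". For the escalating arm's first randomized week, the Group 3 description states: "They will be given 3.125 mg tablets to take bid for 1 week". The dose then goes to 6.25 mg, 12.5 mg and optionally 25 mg bid.

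**First reduction.** A. Study Design gives the general rule: "If a dose is not tolerated, the dose will be decreased to the prior week's tolerated dose for the remainder of the study". Under Double-blinded Randomized Phase, the blinded physician asks the research pharmacist for a reduction: "He will provide a new week's worth of medications at the" dose described there as lower. For the fixed low-dose arm the same section says: "In the case of fixed low-dose of carvedilol, placebo will be provided". For the escalating arm, Blinded Medication Dispensing says "subjects on dose-escalating carvedilol will be provided a new bottle of carvedilol at the prior week's dose", and adds that no further escalation follows a reduction.

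**Later reductions.** If the problem persists, "subjects on dose-escalating carvedilol will be provided a new bottle of carvedilol at half the current reduced dose". Of reductions overall, "only 3 total dose reductions will be allowed during the entire 6 month study". A patient still intolerant after the third is taken off study drug.

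**Leaving the study.** H. Early Withdrawal lists needing more than three reductions among the reasons for which a patient may be withdrawn from the study. It makes no distinction between arms.

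**Endpoint schedule.** The Primary Aim names erythropoietin and FDG-PET uptake as co-primary endpoints. In Table 1, erythropoietin falls in the column for months 3 and 6 or study exit. FDG-PET is in the same column but marked for 6 months only, and the FDG-PET scan section gives baseline and 6 months as the two scan times.

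**The concern.** There are two separate problems.

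**Week 1, escalating arm.** A reduction is triggered by signs such as a seated systolic pressure under 85 mm Hg, a resting pulse under 50, or a heart-failure admission. The dose of a patient who meets a trigger ought to fall. In week 1 of this arm, the dose the rule points back to is the dose the patient is already taking. The physician does not know the arm and the new bottle is labelled as a reduction, so the physician would assume lower exposure when exposure is unchanged. After the run-in, routine calls are weekly, not daily.

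**After three reductions, any arm.** One section stops drug only; another permits removal from the study for the same reason. If the second is applied before month 6, the patient has no second FDG-PET and no 6-month-to-baseline ratio. These patients are selected for intolerance, so their absence could bias a comparison that the protocol says will be intent-to-treat whatever dose changes occur. The Analysis Plan gives no method for a missing scan.

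**Working it through.** The plan states no figure for either problem. The only plan figures used are the dose schedule and the number randomized.

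**Step 1. Arm size.** C. Sample Size Rationale gives 14 per group, 10% dropout after randomization and 48 randomized. 14 / 0.9 = 15.6, rounded up to 16 per arm; 16 × 3 = 48, which reproduces the plan. After the planned dropout, 48 × 0.9 / 3 = 14.4 per arm.

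**Step 2. Trace the escalating-arm rule.** Let R1 be the prior week's dose, R2 = R1/2, and R3 = R2/2 (the halving rule applied again). Doses are mg bid, with intolerance first appearing in the first week at each level:

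| Dose when intolerant | Dose the week before | R1 | R2 | R3 |
|---|---|---|---|---|
| 3.125 (week 1) | 3.125 (run-in) | 3.125 | 1.56 | 0.78 |
| 6.25 (week 2) | 3.125 | 3.125 | 1.56 | 0.78 |
| 12.5 (week 3) | 6.25 | 6.25 | 3.125 | 1.56 |
| 25 | 12.5 | 12.5 | 6.25 | 3.125 |

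Only in the first row does R1 equal the current dose. There the reduction cancels the planned rise to 6.25 mg but lowers nothing.

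**Step 3. Compare arms in week 1.** Both active arms are on 3.125 mg bid, or 2 × 3.125 = 6.25 mg/day. After the first reduction:
- escalating arm: 2 × 3.125 = 6.25 mg/day;
- fixed low-dose arm: 0 mg/day.

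A replacement week is 7 × 2 = 14 doses at the unchanged level unless the patient calls sooner.

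**Step 4. How often.** The plan gives no week 1 intolerance rate. Purely as an assumption, for a rate p among 16 patients, the expected number is 16p and the chance of at least one is 1 − (1 − p)^16:

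| Assumed p | Expected patients | Chance of at least one |
|---|---|---|
| 1% | 0.16 | 15% |
| 5% | 0.8 | 56% |
| 10% | 1.6 | 81% |

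**Step 5. The scan.** Setting the sections side by side: Blinded Medication Dispensing stops drug; H. Early Withdrawal permits leaving the study; Table 1 offers erythropoietin at exit but gives no exit time for FDG-PET. A patient withdrawn early could therefore have a second value for one co-primary endpoint and none for the other. Each such patient is 1/16 = 6.25% of an arm's randomized patients.

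**The case against.** **The patient is not left unprotected.** A reader might infer that a week 1 patient with severe hypotension has no recourse. The documents do not support that. H. Early Withdrawal lets the investigator withdraw a patient for toxicity with no prior reduction, and the section on carvedilol risks says the same. This stands, and limits the safety weight. It does not repair the dose-reduction step, which exists so that a patient need not be withdrawn.

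**The intent is plainly a lower dose.** Study Design and the pharmacist instruction show that a real step down is meant. This also answers a wider inference, that the rule fails at every level because a patient stable for some weeks has the same dose in the prior week. Above 3.125 mg there is a lower, previously tolerated level to return to, so the intent can be carried out. In week 1 there is none: the run-in dose is the current dose, and no level below it is named for a first reduction.

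**No floor on halving.** A reader might count this as an error. It is a preference. The cap of three bounds the path near 0.78 mg bid, nothing in the documents shows such doses to be unsafe or impractical, and a small active dose is defensible in an arm aiming at the maximum tolerated dose.

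**The scan may not be lost.** Withdrawal is permitted, not required, and the Table 1 mark may be there only to exclude month 3. Both points stand, so the loss is possible, not certain. The FDG-PET scan section nevertheless names only baseline and 6 months.

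**Conclusion.** Both points hold, at modest weight, and should be corrected.

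1. In the escalating arm, a first reduction in week 1 leaves 6.25 mg/day unchanged and spends one of three reductions, against 0 mg/day for the same signs in the low-dose arm. This rests on the text alone. It concerns 1 of 24 weeks and patients who have just tolerated the dose, so it should be uncommon; the frequencies shown are assumptions.

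2. In all three arms, not only the escalating one, the conflict between stopping drug and leaving the study could remove 6-month FDG-PET values selectively from intolerant patients. It requires persistent intolerance after three reductions and then a discretionary withdrawal, and the plan gives no rate for either.

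A reader might infer that the trial's power is compromised. The documents do not support that: the stated calculation covers placebo against low dose, it already allows 10% dropout, and no rate of this kind of loss is given. The concern is selective missingness.

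**What to change.** **Week 1 step.** In Double-blinded Randomized Phase and Blinded Medication Dispensing, state: *In the escalating arm a first dose reduction is to the next lower dose level; for a patient on 3.125 mg bid, including in week 1, placebo is dispensed, as in the low-dose arm.* Any further reduction for that patient re-dispenses placebo. A floor of 3.125 mg before placebo on later halvings is optional; it would treat a patient brought down to 3.125 mg like one who started there.

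**Retention.** In H. Early Withdrawal, change the item on needing more than three reductions from a reason for leaving the study to a reason for stopping study drug; otherwise it would conflict with the next sentence. There and in Blinded Medication Dispensing, add: *Patients in any arm taken off study drug for intolerance remain in follow-up through the month 3 and 6 assessments, including the 6-month FDG-PET, unless they withdraw consent or a scan is unsafe.*

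**Cost.** A few lines of protocol text and revised pharmacy instructions. No extra patients are needed, the 6-month scan is already scheduled, and the existing encapsulation and bottle labelling still serve. The real downside is that an escalating-arm patient reduced in week 1 loses 3.125 mg bid and, with no re-escalation, stays on placebo for the rest of the study while analysed in the escalating arm.
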